3.2 Exclusion Criteria

1. Involvement in the planning and/or conduct of the study (applies to both AstraZeneca staff and/or staff at the study site). Previous enrollment in the present study.
2. Participation in another clinical study with an investigational product for cancer during the last 12 months.
3. Any previous treatment with a PD1 or PD-L1 inhibitor, including durvalumab.
4. Symptomatic or uncontrolled brain metastases requiring concurrent treatment, inclusive of but not limited to surgery, radiation and/or corticosteroids, in excess of prednisone 10 mg/d or equivalent.
5. Sensitizing mutations in *EGFR* or rearrangements in *ALK* or *ROS1*.
6. History of allergic reactions attributed to compounds of similar chemical or biologic composition to durvalumab.
7. Current or prior use of immunosuppressive medication within 28 days before the first dose of durvalumab, with the exceptions of intranasal and inhaled corticosteroids. Patients may be on systemic corticosteroids provided the dose does not exceed prednisone 10 mg/d or equivalent for 1 week prior to study drug administration.

HCC #:16-054

Version Date: 008/11/2020

8. Active autoimmune disease requiring systemic treatment within the past 2 years.
NOTE: Subjects with autoimmune disease, such as vitiligo, Grave's disease, or psoriasis not requiring systemic treatment (within the past 2 years) are not excluded.
9. Active or prior documented inflammatory bowel disease (e.g., Crohn's disease, ulcerative colitis).
10. History of primary immunodeficiency.
11. History of allogeneic organ transplant.
12. Uncontrolled intercurrent illness including, but not limited to, ongoing or active infection, symptomatic congestive heart failure, uncontrolled hypertension, unstable angina pectoris, cardiac arrhythmia, active peptic ulcer disease or gastritis, active bleeding diatheses including any subject known to have evidence of acute or chronic hepatitis B, hepatitis C or human immunodeficiency virus (HIV), or psychiatric illness/social situations that would limit compliance with study requirements or compromise the ability of the subject to give written informed consent.
13. Known history of previous clinical diagnosis of tuberculosis.
14. History of leptomeningeal carcinomatosis.
15. Receipt of live attenuated vaccination within 30 days prior to study entry or within 30 days of receiving durvalumab.
16. Any condition that, in the opinion of the investigator, would interfere with evaluation of study treatment or interpretation of patient safety or study results.
17. Subjects with uncontrolled seizures.
18. Pregnant women are excluded from this study because durvalumab is associated with the potential for teratogenic or abortifacient effects. Because there is an unknown but potential risk for adverse events in nursing infants secondary to treatment of the mother with durvalumab, breastfeeding should be discontinued if the mother is treated with durvalumab.
19. Prior history of radiation pneumonitis.

3.3 Inclusion of Women and Minorities

Both men and women of all races and ethnic groups are eligible for this trial.

4. REGISTRATION PROCEDURES

4.1 General Guidelines

Eligible patients will be entered on study centrally by the Study Coordinator. Following registration, patients should begin protocol treatment within 5 days. Issues that would cause treatment delays should be discussed with the Investigator. The Study Coordinator should be notified of cancellations as soon as possible.

4.2 Registration Process

Once the signed informed consent has been obtained, all pretreatment evaluations have been performed, and patient's eligibility has been confirmed by the coordination team and the treating physician investigator, a patient will be entered on study. To register a patient, the research nurse or data manager must complete the eligibility/registration form and review the signed Informed Consent, and HIPAA authorization form.

To complete the registration process, the research nurse or data manager will:

- Verify the eligibility
- Register the patient on study
- Assign a patient accession number

5. STUDY PROCEDURES

Before study entry, throughout the study, and following study drug discontinuation, various clinical and diagnostic laboratory evaluations are outlined. The purpose of obtaining these detailed measurements is to ensure adequate safety and tolerability assessments. Clinical evaluations and laboratory studies may be repeated more frequently if clinically indicated. The Schedules of Assessments during the screening and treatment period is provided following the Protocol Synopsis and Section 11.

5.1 Screening Phase

Screening procedures will be performed up to 28 days before Day 1, unless otherwise specified. All subjects must first read, understand, and sign the IRB/REB/IEC-approved ICF before any study-specific screening procedures are performed. After signing the ICF, completing all screening procedures, and being deemed eligible for entry, subjects will be enrolled in the study. Procedures that are performed prior to the signing of the ICF and are considered standard of care may be used as screening assessments if they fall within the 28-day screening window.

The following procedures will be performed during the Screening Visit:

- Verification of Informed Consent
- Review of eligibility criteria
- Medical and surgical, oncologic history and demographics, tobacco and alcohol use
- Complete physical exam
- ECOG Performance Status

- Vitals signs (temperature, blood pressure, pulse rate, respiratory rate), weight, pulse oximetry
- Verification of tumor biopsy
- Review of prior/concomitant medications
- Imaging by CT/MRI
- Adverse event/Serious adverse event assessment
- Clinical laboratory tests for:
 - Hematology (see Table below)
 - Clinical chemistry (see Table below)
 - TSH
 - Coagulation (PT, PTT, INR)
 - Creatinine Clearance
 - Serum pregnancy test (for women of childbearing potential only)
 - , Hepatitis B surface antigen, hepatitis C antibody and HIV serologies
 - Urinalysis (see Table below)

5.2 Treatment Phase

Procedures to be conducted during the treatment phase of the study are presented in the Schedule of Assessments, section 11. Pre-menopausal female subjects of childbearing potential must have a negative urine hCG or serum β hCG checked within 24 hours of 1st durvalumab administration.

5.3 End of Treatment

End of treatment is defined as the last planned dosing visit within the 12-month dosing period. For subjects who discontinue durvalumab prior to 12 months, end of treatment is considered the last visit where the decision is made to discontinue treatment. All required procedures may be completed within \pm 7 days of the end of treatment visit. Repeat disease assessment is not required if performed within 28 days prior to the end of treatment visit.

Assessments for subjects who have completed durvalumab treatment and achieved disease control, or have discontinued durvalumab due to toxicity in the absence of confirmed progressive disease are provided in APPENDIX E.

Assessments for subjects who have discontinued durvalumab treatment due to confirmed PD are presented in APPENDIX F.

5.4 Description of procedures

5.4.1 Medical history and physical examination, weight and vital signs

Findings from medical history (obtained at screening) and physical examination shall be given a baseline grade according to the procedure for AEs. Increases in severity of pre-existing conditions during the study will be considered AEs, with resolution occurring when the grade returns to the pre-study grade or below.

Physical examinations will be performed on study days noted in the Schedule of Assessments.

A complete physical examination will be performed and will include an assessment of the following (as clinically indicated): general appearance, respiratory, cardiovascular, abdomen, skin, head and neck (including ears, eyes, nose and throat), lymph nodes, thyroid, musculo-skeletal (including spine and extremities), genital/rectal, and neurological systems and at screening only, height.

Vital signs (temperature, blood pressure, pulse rate, respiratory rate, and pulse oximetry) will be measured per institutional standard of care or as clinically indicated, as noted in the Schedule of Assessments.

5.4.2 Clinical Laboratory Tests

The following clinical laboratory tests will be performed (see the Schedule of Assessments, Appendix E and Appendix F for the timepoints of each test):

- Coagulation parameters: Prothrombin time, activated partial thromboplastin time and International normalized ratio to be assessed at baseline and as clinically indicated
- Pregnancy test (female subjects of childbearing potential only)
 - Serum beta-human chorionic gonadotropin (at screening and as clinically indicated during treatment)
- Thyroid Stimulating Hormone (TSH)
 - free T3 and free T4 only if TSH is abnormal
- Other laboratory tests
 - Hepatitis B surface antigen, hepatitis C antibody
 - HIV antibody

Hematology Laboratory Tests

Basophils	Mean corpuscular volume
Eosinophils	Monocytes
Hematocrit	Neutrophils
Hemoglobin	Platelet count
Lymphocytes	Red blood cell count
Mean corpuscular hemoglobin	Total white cell count
Mean corpuscular hemoglobin concentration	

Clinical chemistry (Serum or Plasma) Laboratory Tests

Albumin	Glucose
Alkaline phosphatase	Lactate dehydrogenase

HCC #:16-054

Version Date: 008/11/2020

Clinical chemistry (Serum or Plasma) Laboratory Tests

Albumin	Glucose
Alanine aminotransferase	Lipase
Amylase	Magnesium
Aspartate aminotransferase	Potassium
Bicarbonate	Sodium
Calcium	Total bilirubin ^a
Chloride	Total protein
Creatinine	Urea or blood urea nitrogen, depending on local practice
Gamma glutamyltransferase ^b	Uric acid

^a If Total bilirubin is $\geq 2x$ ULN (and no evidence of Gilbert's syndrome) then fractionate into direct and indirect bilirubin

^b At baseline and as clinically indicated

Urinalysis Tests^a

Bilirubin	pH
Blood	Protein
Glucose	Specific gravity
Ketones	Colour and appearance

^a Microscopy should be used as appropriate to investigate white blood cells with use of the high power field for red blood cells

6. TREATMENT PLAN

6.1 Durvalumab Administration

Treatment will be administered on an outpatient basis. No investigational or commercial agents or therapies other than those described below may be administered with the intent to treat the patient's malignancy.

Regimen Description					
Agent	Premedications / Precautions	Dose	Route	Schedule	Cycle Length
Durvalumab	N/A	** in 500 cc NS	IV over 60 minutes (± 5 minutes)	Day 1	28 days (4 weeks)

** Dose calculation is based in patient weight at the time of each treatment. See section 6.1.1 for fixed dose information for subjects weighing greater than or equal to 30 kg and Appendix C for calculation of dose for subjects with weight of less than 30 kg.

Study drug preparation

For patients weighing ≥ 30 kg, a fixed dose of 1500 mg Q4W durvalumab (equivalent to 20 mg/kg Q4W) (based on an average body WT of 75 kg) should be prepared. For subjects <30 kg body weight, dose is determined using body mass, calculating the stock volume of durvalumab to achieve the accurate dose according to Appendix C.

Preparation of durvalumab doses for administration with an IV bag

The dose of durvalumab for administration must be prepared by the Investigator's or site's designated IP manager using aseptic technique. Total time from needle puncture of the durvalumab vial to the start of administration should not exceed:

- 24 hours at 2°C to 8°C (36°F to 46°F)
- 4 hours at room temperature

If in-use storage time exceeds these limits, a new dose must be prepared from new vials. Infusion solutions must be allowed to equilibrate to room temperature prior to commencement of administration.

No incompatibilities between durvalumab and polyvinylchloride or polyolefin IV bags have been observed. Dose of 1500mg durvalumab for patients >30 kg will be administered using an IV bag containing 0.9% (w/v) saline or 5% (w/v) dextrose for IV infusion with a final durvalumab concentration ranging from 1 to 20 mg/mL, and delivered through an IV administration set with a 0.2- or 0.22- μm in-line filter.

Remove a volume of IV solution from the IV bag equal to the calculated volume of durvalumab to be added to the IV bag prior to addition of durvalumab. Next, the volume of durvalumab (i.e., 30.0 mL for 1500 mg of durvalumab) is added to the IV bag such that final concentration is within 1 to 20 mg/mL (IV bag volumes 100 to 1000 mL). Mix the bag by gently inverting to ensure homogeneity of the dose in the bag.

Patient weight at baseline should be used for dosing calculations in patients ≤ 30 kg unless there is a $\geq 10\%$ change in weight. Dosing day weight can be used for dosing calculations instead of baseline weight per institutional standard.

For patients <30 kg, Calculate the dose volume of durvalumab and number of vials needed for the subject to achieve the accurate dose according to Appendix C.

Durvalumab will be administered at room temperature (approximately 25°C) by controlled infusion via an infusion pump into a peripheral or central vein. Following preparation of durvalumab, the entire contents of the IV bag should be administered as an IV infusion over approximately 60 minutes (± 5 minutes), using a 0.2, or 0.22- μm in-line filter. Less than 55 minutes is considered a deviation.

HCC #:16-054

Version Date: 008/11/2020

The IV line will be flushed with a volume of IV solution (0.9% [w/v] saline) equal to the priming volume of the infusion set used after the contents of the IV bag are fully administered, or complete the infusion according to institutional policy to ensure the full dose is administered and document if the line was not flushed.

Standard infusion time is 1 hour. However, if there are interruptions during infusion, the total allowed time should not exceed 8 hours at room temperature. The table below summarizes time allowances and temperatures.

Durvalumab hold and infusion times

Maximum time from needle puncture to start of administration	4 hours at room temperature, 24 hours at 2°C to 8°C
Maximum time for IV bag infusion, including interruptions	8 hours at room temperature

In the event that either preparation time or infusion time exceeds the time limits outlined above, a new dose must be prepared from new vials. Durvalumab does not contain preservatives, and any unused portion must be discarded.

Monitoring of dose administration

Subjects will be monitored before, during and after the infusion with assessment of vital signs per institutional standard of care or as clinically indicated, as noted in the Schedule of Assessment. Subjects are monitored (pulse rate, blood pressure) every 30 minutes during the infusion period (including times where infusion rate is slowed or temporarily stopped).

In the event of a ≤Grade 2 infusion-related reaction, the infusion rate of study drug may be decreased by 50% or interrupted until resolution of the event (up to 4 hours) and re-initiated at 50% of the initial rate until completion of the infusion. For subjects with a ≤Grade 2 infusion-related reaction, subsequent infusions may be administered at 50% of the initial rate. Acetaminophen and/or an antihistamine (e.g., diphenhydramine) or equivalent medications per institutional standard may be administered at the discretion of the investigator. If the infusion-related reaction is Grade 3 or higher in severity, study drug will be discontinued. The standard infusion time is one hour, however if there are interruptions during infusion, the total allowed time from infusion start to completion of infusion should not exceed 4 hours at room temperature, with maximum total time at room temperature not exceeding 4 hours (otherwise requires new infusion preparation).

As with any antibody, allergic reactions to dose administration are possible. Appropriate drugs and medical equipment to treat acute anaphylactic reactions must be immediately available, and study personnel must be trained to recognize and treat anaphylaxis. The study site must have immediate access to emergency resuscitation teams and equipment in addition to the ability to admit subjects to an intensive care unit if necessary.

6.2 General Concomitant Medication and Supportive Care Guidelines

HCC #:16-054

Version Date: 008/11/2020

Investigators may prescribe concomitant medications or treatments (e.g., acetaminophen, diphenhydramine) deemed necessary to provide adequate prophylactic or supportive care except for those medications identified as “excluded” as listed below.

Excluded Concomitant Medications

The following medications are considered exclusionary during the study.

1. Any investigational anticancer therapy other than the protocol specified therapy.
2. Any concurrent chemotherapy, radiotherapy (except palliative radiotherapy), immunotherapy, biologic or hormonal therapy for cancer treatment. Concurrent use of hormones for non-cancer related conditions (e.g., insulin for diabetes and hormone replacement therapy) is acceptable. NOTE: Local treatment of isolated lesions for palliative intent is acceptable (e.g., by local surgery or radiotherapy).
3. Immunosuppressive medications including, but not limited to systemic corticosteroids at doses not exceeding 10 mg/day of prednisone or equivalent, methotrexate, azathioprine, and TNF- α blockers. Use of immunosuppressive medications for the management of investigational product-related AEs or in subjects with contrast allergies is acceptable. In addition, use of inhaled and intranasal corticosteroids is permitted. A temporary period of steroids will be allowed for different indications, at the discretion of the principal investigator (e.g., chronic obstructive pulmonary disease, radiation, nausea, etc).
4. Live attenuated vaccines within 30 days of durvalumab dosing (ie, 30 days prior to the first dose, during treatment with durvalumab and for 30 days post discontinuation of durvalumab. Inactivated vaccines, such as the injectable influenza vaccine, are permitted.

Rescue Medications	
Rescue/supportive medication/class of drug:	Usage:
Concomitant medications or treatments (eg, acetaminophen or diphenhydramine) deemed necessary by the Investigator to provide adequate prophylactic or supportive care, except for those medications identified as “prohibited” as listed above	To be administered as prescribed by the Investigator
Best supportive care (including antibiotics, nutritional support, growth factor support, correction of metabolic disorders, optimal symptom control, and pain management [including palliative radiotherapy, etc])	Should be used when necessary for all patients

Contraception

Females of childbearing potential who are sexually active with a nonsterilised male partner must use 2 methods of effective contraception (see below) from screening, and for at least 90 days following the last infusion of durvalumab; cessation of birth control after this point should be

discussed with a responsible physician. Periodic abstinence, the rhythm method, and the withdrawal method are not acceptable methods of birth control.

- Females of childbearing potential are defined as those who are not surgically sterile (i.e., bilateral tubal ligation, bilateral oophorectomy, or complete hysterectomy) or postmenopausal (defined as 12 months with no menses without an alternative medical cause).
- Nonsterilised males who are sexually active with a female partner of childbearing potential must use 2 acceptable methods of effective contraception (see below) from screening and for 90 days after receipt of the final dose of investigational product.

Effective methods of contraception (two methods must be used)

Barrier Methods	Intrauterine Device Methods	Hormonal Methods
Male condom plus spermicide Cap plus spermicide	Copper T Progesterone T ^a	Implants Hormone shot or injection
Diaphragm plus spermicide	Levonorgestrel-releasing intrauterine system (e.g., Mirena [®]) ^a	Combined pill Minipill Patch

^a This is also considered a hormonal method.

Blood donation

Subjects should not donate blood while participating in this study and for at least 90 days following the last infusion of durvalumab.

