3. PATIENT SELECTION

3.1 Inclusion Criteria

1. Written informed consent and any locally-required authorization (e.g., HIPAA) obtained from the subject prior to performing any protocol-related procedures, including screening evaluations
2. Patients must have histologically or cytologically confirmed Stage IIIB or IV (American Joint Committee on Cancer, 7th edition; AJCC 7) non-small cell lung cancer.
3. Patients must have measurable disease, defined as at least one lesion that can be accurately measured in at least one dimension (longest diameter to be recorded for non-nodal lesions and short axis for nodal lesions) as ≥ 20 mm with conventional techniques or as ≥ 10 mm with spiral CT scan, MRI, or calipers by clinical exam. See Section 12 for the evaluation of measurable disease.

4. Patients must have not have received any prior therapy (chemotherapy, immunotherapy, endocrine therapy, targeted therapy, biologic therapy, tumor embolization, monoclonal antibodies, other investigational agent) for the treatment of stage IV NSCLC. Patients may have received prior adjuvant or neoadjuvant chemotherapy or chemotherapy given as part of a curative intent chemoradiotherapy approach for NSCLC, if the last administration of the prior regimens occurred at least 1 year prior to study entry.
5. Age \geq 18 years at time of study entry.

Because no dosing or adverse event data are currently available on the use of durvalumab in patients <18 years of age, children are excluded from this study.

6. ECOG performance status of 2 (Appendix A).
7. Life expectancy of greater than 12 weeks.
8. Tissue available (archived or fresh tumor biopsy) for the PD-L1 assay.
9. Patients must have normal organ and marrow function as defined below:
 - Absolute neutrophil count (ANC) $\geq 1.5 \times 10^9/L$ (> 1500 per mm^3)
 - Hemoglobin ≥ 9.0 g/dL
 - Platelet count $\geq 100 \times 10^9/L$ ($>100,000$ per mm^3)
 - Serum bilirubin ≤ 1.5 x institutional upper limit of normal (ULN). This will not apply to subjects with confirmed Gilbert's syndrome (persistent or recurrent hyperbilirubinemia that is predominantly unconjugated in the absence of hemolysis or hepatic pathology), who will be allowed only in consultation with their physician.
 - AST (SGOT)/ALT (SGPT) ≤ 2.5 x institutional upper limit of normal unless liver metastases are present, in which case it must be ≤ 5 x ULN

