12.1.2 Disease Parameters

Measurable disease. Measurable lesions are defined as those that can be accurately measured in at least one dimension (longest diameter to be recorded) as ≥ 20 mm by chest x-ray or as ≥ 10 mm with CT scan, MRI, or calipers by clinical exam. All tumor measurements must be recorded in millimeters (or decimal fractions of centimeters).

Note: Tumor lesions that are situated in a previously irradiated area might or might not be considered measurable.

Malignant lymph nodes. To be considered pathologically enlarged and measurable, a lymph node must be ≥ 15 mm in short axis when assessed by CT scan (CT scan slice thickness recommended to be no greater than 5 mm). At baseline and in follow-up, only the short axis will be measured and followed.

Non-measurable disease. All other lesions (or sites of disease), including small lesions (longest diameter <10 mm or pathological lymph nodes with ≥ 10 to <15 mm short axis), are considered non-measurable disease. Bone lesions, leptomeningeal disease, ascites, pleural/pericardial effusions, lymphangitis cutis/pulmonitis, inflammatory breast disease, and abdominal masses (not followed by CT or MRI), are considered as non-measurable.

Note: Cystic lesions that meet the criteria for radiographically defined simple cysts should not be considered as malignant lesions (neither measurable nor non-measurable) since they are, by definition, simple cysts.

‘Cystic lesions’ thought to represent cystic metastases can be considered as measurable lesions, if they meet the definition of measurability described above. However, if non-cystic lesions are present in the same patient, these are preferred for selection as target lesions.

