12.1.4 Response Criteria

12.1.4.1 Evaluation of Target Lesions

Complete Response (CR): Disappearance of all target lesions. Any pathological lymph nodes (whether target or non-target) must have reduction in short axis to <10 mm.

Partial Response (PR): At least a 30% decrease in the sum of the diameters of target lesions, taking as reference the baseline sum diameters.

Progressive Disease (PD): At least a 20% increase in the sum of the diameters of target lesions, taking as reference the smallest sum on study (this includes the baseline sum if that is the smallest on study). In addition to the relative increase of 20%, the sum must also demonstrate an absolute increase of at least 5 mm. (Note: the appearance of one or more new lesions is also considered progressions).

Stable Disease (SD): Neither sufficient shrinkage to qualify for PR nor sufficient increase to qualify for PD, taking as reference the smallest sum diameters while on study.

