14.3 Analysis plan

Summary tables describing the patient cohort will be compiled, including:

- Demographics (age, sex, race, ethnicity, smoking history, recent weight loss)
- Disease history (current stage, tumor sites, histology)
- Comorbidities at start of therapy (cardiac, pulmonary, other)
- PD-L1 expression status

Analysis of primary endpoints:

- The OS curve, median OS, and a 90% confidence interval for the median OS will be estimated by standard methods (the Kaplan-Meier method for survival, and the Greenwood variance formula applied to log-transformed survival) in the efficacy cohort (primary analysis) and safety cohort (sensitivity analysis). Durvalumab will be considered a promising therapy in this population if the estimated median OS is 9 months or greater, and/or the lower bound of a 90% confidence interval for the median OS is greater than 5 months. However, these results will be interpreted in the context of safety data and the presence of durable responses attributed to study therapy.).
- All adverse events that are determined to be possibly, probably or definitely related to treatment will be tabulated according to grade and type, in order of frequency in the safety cohort. Each adverse event will be counted only once per patient, with the highest grade recorded. Serious adverse events and adverse events of special interest (ASEI, defined in section 8.1.3) will also be tabulated by frequency. Listings will be provided for all on-study deaths and adverse events that lead to withdrawal from study.

Lilenbaum et al (2008) observed a rate of grade ≥ 3 adverse events of 41% (90% CI 31%-53%) for a platinum-based doublet, and 27% (90% CI 18%-38%) for erlotinib. In this context of balancing expected toxicity and efficacy, a rate of grade ≥ 3 treatment related adverse events of 30% or less would be acceptable, especially if associated with efficacy in individuals. In a cohort of n=50, a 30% rate of grade ≥ 3 adverse events would have a 90% CI of (21%-41%), demonstrating it is likely more tolerable than the platinum doublet.

Secondary Objectives:

HCC #:16-054

Version Date: 008/11/2020

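### No rule says how a target lesion irradiated or resected on study is scored, so shrinkage from palliative local treatment can count as a partial response

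*Combined protocol and SAP*

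**What the plan says.** **Treatment on study.** Section 6.2, item 2 of the excluded medications, prohibits "Any concurrent chemotherapy, radiotherapy (except palliative radiotherapy), immunotherapy, biologic or hormonal therapy for cancer treatment". Its note adds: "Local treatment of isolated lesions for palliative intent is acceptable (e.g., by local surgery or radiotherapy". Nothing separates target from non-target lesions. The rescue table in 6.2 lists palliative radiotherapy under best supportive care, and the study calendar (Section 11) and Appendices E and F each carry a row for it.

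**Treatment before study.** Inclusion criterion 4 (Section 3.1) names the barred prior therapies as "chemotherapy, immunotherapy, endocrine therapy, targeted therapy, biologic therapy, tumor embolization, monoclonal antibodies, other investigational agent) for the treatment of stage IV NSCLC"; radiotherapy is not on the list. Earlier (neo)adjuvant chemotherapy or curative-intent chemoradiotherapy is allowed "if the last administration of the prior regimens occurred at least 1 year prior to study entry". Exclusion criterion 4 (Section 3.2) removes patients with "Symptomatic or uncontrolled brain metastases requiring concurrent treatment, inclusive of but not limited to surgery, radiation and/or corticosteroids". No interval is given for stand-alone or palliative radiotherapy elsewhere in the body.

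**Lesion rules.** Section 12.1.2 notes: "Tumor lesions that are situated in a previously irradiated area might or might not be considered measurable". No deciding rule follows. Section 12.1.4.1 defines partial response as "At least a 30% decrease in the sum of the diameters of target lesions, taking as reference the baseline sum diameters", with no exception for a lesion treated locally.

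**Analysis.** ORR and PFS are secondary and are also reported by PD-L1 status. Section 14.3 says the survival result will be read in the context of safety and "the presence of durable responses attributed to study therapy".

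**The concern.** Response is meant to reflect the drug. Radiotherapy or surgery to a target lesion changes the target sum for another reason, and in a single-arm trial no comparator shows how much of the response rate comes from it. The rules on evaluability (12.1.1), target selection (12.1.2), best response (12.1.4.3), PFS (12.1.6) and analysis (14.3) contain no exclusion, censoring or sensitivity analysis for local treatment.

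There are two separate gaps. One concerns selection: whether a lesion irradiated before baseline may be a target. The other concerns scoring: what happens to a target lesion treated after Day 1. At stake are ORR, overall and in the smaller PD-L1 groups, the timing of progression, and the durable responses that Section 14.3 uses as context for the survival result. That section gives no rule for attributing a response to study therapy.

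**Working it through.** **1. The plan's own figures.** The documents give no sample size, threshold or power for ORR. The survival power in Section 14.1 was reproduced by simulating 20,000 trials per setting: exponential survival with median 9 months, N=50, uniform 18-month accrual plus 6 months of follow-up, and Kaplan-Meier limits with Greenwood variance on log survival. Power for the interval to exclude 5 months is 85.6% (90% CI) and 78.3% (95% CI), against the stated 85% and 78%. No input is a tumour measurement, so this point does not touch it. The 90% Wilson interval for 15/50 is 20.6% to 41.5%, in line with the 21% to 41% in Section 14.3; the same formula is used below.

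**2. Can local treatment alone meet the partial response rule?** Change = (new sum - baseline sum) / baseline sum, with every other lesion unchanged. The lesion sizes are illustrative.
- 30 mm lesion resected from a 100 mm sum: (70 - 100)/100 = -30.0%. Meets PR.
- 20 mm lesion resected from a 60 mm sum: (40 - 60)/60 = -33.3%. Meets PR.
- Sole 40 mm lesion irradiated to 25 mm: (25 - 40)/40 = -37.5%. Meets PR.

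Confirmation at 4 weeks or more (Section 11, footnote k; Section 12.1.4.3) does not filter this out if the reduction persists, and after resection it does.

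**3. Effect on ORR.** Assume all 50 patients are evaluable and k patients respond only through local treatment. Each adds 1/50 = 2 points. Section 2.3 cites 14% for durvalumab in NSCLC (7/50) and 23-29% for first-line PD1/PD-L1 monotherapy (13/50 = 26% is the midpoint).

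| k (assumed) | From 7/50: ORR (90% Wilson) | From 13/50: ORR (90% Wilson) |
|---|---|---|
| 0 | 14% (7.8-23.9) | 26% (17-37) |
| 1 | 16% (9.3-26.2) | 28% (19-39) |
| 2 | 18% (10.8-28.5) | 30% (21-41) |
| 3 | 20% (12.3-30.7) | 32% (22-44) |

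In a PD-L1 subgroup of size m, each such patient adds 1/m. With m=25, which is an assumption, that is 4 points.

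**4. Effect on PFS.** Section 12.1.4.1 measures progression from the smallest sum on study: at least 20% and at least 5 mm.
- *Earlier.* With no treatment, a 100 mm nadir needs 120 mm, which is 20 mm of growth. After a 30 mm lesion is resected the nadir is 70 mm and progression needs 1.2 × 70 = 84 mm, which is 14 mm of growth in the remaining lesions.
- *Later.* Take the same 100 mm sum as 70 mm stable plus one 30 mm lesion that would grow to 50 mm. Untreated, the sum reaches 120 mm and is progression. If that lesion is treated first, this event does not occur.

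New lesions, unequivocal non-target progression and death remain events in both cases.

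**The case against.** The strongest reply is that the documents nowhere say such shrinkage is a durvalumab response. Section 12.1 adopts RECIST 1.1, and the guideline itself, which is not among the documents, may say more. Response is secondary and descriptive, with no threshold. Section 14.3 itself speaks of attribution, so a sensible reader would not credit an irradiated lesion, and the radiotherapy row should let such patients be identified at reporting.

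Much of this limits the point. A reader might infer several stronger things that the text does not support:
- *That any lesion may be treated.* The permission is for isolated lesions with palliative intent.
- *That prior radiotherapy has no washout at all.* A curative-intent chemoradiotherapy regimen carries 1 year. Criterion 4 also opens by barring any prior therapy for stage IV disease, so its silence on radiotherapy is ambiguous, not openly permissive.
- *That PFS is inflated.* Step 4 shows either direction is possible.
- *That disappearance of targets gives an overall CR.* That also needs non-target CR and no new lesions (12.1.4.3).
- *That the survival conclusion is biased.* Overall survival does not use response.

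The patient counts are also assumed, and every shifted ORR in the table lies inside the corresponding k=0 interval.

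What does not fall away is the scoring gap. Section 12 restates the criteria at length and handles other complications such as effusions and FDG-PET, yet its one sentence on irradiated lesions settles nothing. Discontinuation for alternative anticancer therapy (Section 6.4) does not clearly catch these patients, because 6.2 accepts the treatment. Leaving attribution to judgement after the data are seen is a weak substitute for a rule.

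**Conclusion.** The point holds as a gap in the scoring rules. Applied literally, 12.1.4.1 can score removal or shrinkage of a locally treated target lesion as a partial response, and the resulting ORR error is upward. Its size is 2 points per patient at n=50. The number of such patients is unknown; 1 to 3 is an assumption and would move 14% to 16-20%, or 26% to 28-32%. This assumes that all 50 are evaluable and that these patients would not otherwise have responded. The effect on PFS has no fixed sign. Primary overall survival and its 85% power stand; the only link is the reading of that result beside durable responses. The change should be made because it is cheap, but it concerns secondary endpoints.

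**What to change.** Leave palliative care as it is and change only how lesions count, before responses are analysed.

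1. **Section 12.1.2:** a lesion in a previously irradiated field may be a target only if it has progressed since that radiotherapy.
2. **Section 12.1.4:** a target lesion irradiated or resected on study is not evaluable for response from that date, so its change cannot produce a CR or PR. In the main ORR analysis, best overall response comes from assessments before the local treatment. Add a sensitivity ORR using only the untreated target lesions against their own baseline sum.
3. **PFS:** keep the definition in 12.1.6 and add a sensitivity analysis that counts on-study local treatment of a target lesion as an event.
4. **Data:** record the treated lesion and date for surgery as well as radiotherapy. Radiotherapy has a calendar row; surgery does not.

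The cost is a few sentences, one extra data item and two sensitivity analyses. ORR may come out slightly lower, and a genuine response first seen after local treatment is left out of the main ORR; the untreated-lesion sensitivity analysis shows how much that matters.
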